The Impact of Microbiota and Associated Blood Tryptophan Metabolites on Pain Perception in Patients Undergoing Lumbar Disc Herniation Surgery

Study Follow-Up Table

Study starting from January 12, 2022, following ethical approval:

1. Ethical approval from the DEU Non-Interventional Ethics Committee is estimated to be obtained in 2022.
2. Commencement of patient data recording following the approval of the Ethics Committee.
3. Regular maintenance of records in the SPSS computer program for the purpose of statistical analysis of the acquired data.
4. Estimated completion of results by November 2022.
5. Conducting statistical analysis after data collection.
6. Evaluation of the correlation between tryptophan metabolites (picolinic acid, 3-Hydroxykynurenone, anthranilic acid, kynurenone, quinolinic acid, kynurenic acid, xanthurenic acid) routinely collected in blood samples after lumbar disc herniation surgeries and Visual Analog Scale (VAS) scores.

Document Date: 30.03.2022

Ethic committee decision dated 31.08.2022, numbered 7131-GO

Study Protocol

1. Introduction

The human body is closely associated with a complex ecosystem known as the microbiota. The microbiota encompasses the total of microorganisms found in various regions of the body, from the digestive system to the skin and respiratory system. These microorganisms can have significant effects on health and disease, and recent research indicates that the gut microbiota, in particular, plays a decisive role in pain perception.[1] [2]

In the past decade, research on the influence of gut microbiota on pain has been increasing.[3] The gut microbiota interacts not only with the digestive system but also with the nervous and immune systems.[4] These interactions may modulate pain mechanisms and contribute to chronic pain. Recent research suggests that gut microorganisms may regulate brain function and behaviour.[5] This has been considered an exciting development in the field of anesthesia, because the effect of intestinal microbiota on pain perception offers a new perspective in the development of anesthesia practices.

Tryptophan can be converted into various metabolites by the gut microbiota, and the effects of these metabolites on pain are being investigated. [6] The effect of the gut microbiota on tryptophan metabolism is an important mechanism in regulating pain perception. [7], [8]

An important feature of the microbiota is that the signaling molecules it produces through Tryptophan metabolism can affect pain mechanisms. Some bacteria, especially members of the microbiota such as Escherichia Coli, can produce tryptophan.[9] Furthermore, commensal bacterial species that produce AhR ligands play an important role in regulating AhR activity. [10], [11]. The ability of these bacteria to metabolize Tryptophan can lead to the production of the neurotransmitter tryptamine. [12].

Pain is a subjective experience that cannot be directly observed or measured by biological tests. Therefore, the assessment of pain is largely based on the individual's own subjective interpretation. Although its adequacy in pain assessment is questioned, the method used is generally Visual Analogue Scale (VAS).

In this study, we aimed to examine the effect of microbiota and tryptophan metabolites on pain perception in patients undergoing lumbar disc herniation surgery. We evaluated how the gut microbiota affects pain mechanisms by measuring levels of tryptophan metabolites and assessing pain severity in the pre- and postoperative periods.

2. Materials and Methods

In this study, we adhered to the STROBE (Strengthening the Reporting of Observational Studies in Epidemiology) guidelines to ensure the quality and transparency of the reporting of our observational study.

Our study includes 37 lumbar disc herniation (LDH) surgeries performed in Dokuz Eylül University Faculty of Medicine Central Operating Rooms Brain and Nerve Surgery Hall. For the blood samples in which we evaluated tryptophan metabolites; 2 mL of blood was used from the blood samples taken during routine surgery preparation for the patients and from the routine blood samples taken in the postoperative period, and no additional invasive intervention was performed. We elucidated the relationship between tryptophan metabolites (Picolinic Acid, 3-Hydroxykynurenone, Anthranilic Acid, Kynurenone, Quinolinic Acid, Kynurenic Acid, Xanthurenic Acid) and their variations due to microbiota alterations with VAS in acute pain. Preoperative, postoperative, 8th-hour, and 24th-hour blood samples were routinely collected from patients, with 2 ml of sample material used each time. Concurrently, pain information and vital signs were recorded. After the necessary centrifugation processes, the tryptophan metabolites were analyzed by the relevant laboratory team.

In VAS assessment, patients are typically asked to choose a value between "0, no pain" and "10, the worst imaginable pain." VAS is an 11-point scale (ranging from 0 to 10) that allows patients to numerically express the intensity of their pain.[13]

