2.1. Data Collection

Blood samples were planned and collected from patients during the preoperative evaluation, at the 8th postoperative hour, and at the 24th postoperative hour, adhering to clinical routines for these procedures. Concurrently with each blood draw, the patient's VAS score, the nature of the pain, and vital signs were recorded. At the end of the surgery, procedures were performed in the recovery unit according to the protocols, and the same data along with vital signs were recorded. Blood samples collected from the patients were centrifuged at 4000 rpm for 10 minutes, after which the serum and plasma portions were transferred to Eppendorf tubes. The blood samples were stored at -80°C for preservation. For the same patients, 24-hour postoperative blood collection was performed, and similar data, including VAS scores, were recorded.

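### The title and aim claim an effect of microbiota on pain, but no microbiota measurement is listed and the SAP analyses none, so the metabolite–VAS results cannot support that claim

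*Protocol*

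**What the plan says.** **Claims about microbiota (Protocol)**

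- Title: "The Impact of Microbiota and Associated Blood Tryptophan Metabolites on Pain Perception".
- Section 1, first aim sentence: "we aimed to examine the effect of microbiota and tryptophan metabolites on pain perception". Microbiota is named as a factor alongside the metabolites.
- Section 1, second aim sentence: "We evaluated how the gut microbiota affects pain mechanisms by measuring levels of tryptophan metabolites". The sentence goes on to add assessment of pain severity before and after surgery.
- Section 2, Materials and Methods: the metabolites are related to pain together with "their variations due to microbiota alterations with VAS in acute pain".

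**Rationale.** Section 1 states that "Tryptophan can be converted into various metabolites by the gut microbiota" and cites literature on microbiota, tryptophan metabolism and pain.

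**Operational target.** Item 6 of the Study Follow-Up Table plans "Evaluation of the correlation between tryptophan metabolites" and VAS scores. The SAP's sample-size section sizes the study for the same correlation. Neither mentions microbiota.

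**The concern.** The exposure in the title and aim is not a variable in the study as documented. If the report follows the aim as written, a correlation between a blood metabolite and VAS will be presented as an effect of microbiota on pain. The reverse error is also open: a null correlation could be read as evidence that microbiota does not matter. Neither inference is available when microbiota is not observed. At stake is the study's headline conclusion, not any calculation in it.

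**Working it through.** **1. What the plan's own figure covers.** The SAP gives a minimum of 26 participants (point biserial model, effect size 0.50, alpha 5%, power 80%). It does not state sidedness.

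- Formula: noncentral t with δ = √(N·r²/(1−r²)) and N−2 degrees of freedom.
- With r = 0.50, r²/(1−r²) = 0.25/0.75 = 1/3. At N = 26, δ = √(26/3) = 2.94 on 24 degrees of freedom.
- Two-sided, 26 is the smallest N that reaches 80% (power 0.806), so the plan's figure is reproduced. One-sided, the smallest N is 21.
- At the 37 surgeries given in Protocol section 2, δ = √(37/3) = 3.51 and two-sided power is 0.927.

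These figures describe one metabolite–VAS correlation. No power can be computed for a microbiota effect, because no microbiota exposure is defined.

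**2. Claims against listed data.**

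| Protocol statement | What is attributed to microbiota | Microbiota variable behind it |
|---|---|---|
| Title | Pain perception | None listed |
| Section 1, first aim sentence | Pain perception | None listed |
| Section 1, second aim sentence (the only one of the four to say gut microbiota) | Pain mechanisms | None listed |
| Section 2, methods sentence | Variation in metabolites | None listed |

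Three statements concern pain. The fourth concerns the origin of metabolite variation.

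**3. What is listed (sections 2 to 2.4).** The specimen is blood and the assay is a kynurenine-pathway LC-MS/MS kit. There are seven analytes: picolinic acid, 3-hydroxykynurenone, anthranilic acid, kynurenone, quinolinic acid, kynurenic acid and xanthurenic acid. The other items are VAS, nature of pain, vital signs and routine clinical records.

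**4. The SAP.** The words microbiota, microbial and flora occur 0 times. The patient/control and diagnosis-group comparisons are not defined by microbiota status.

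**5. The exclusions (section 2.2).** There are six, and three bear on the gut or abdomen: previous abdominal surgery, recent antibiotics for intestinal disease, and abdominal conditions thought to change the flora. Only the last mentions flora. All three decide who enters. None gives a microbiota value for an enrolled patient, so they create no recorded contrast to relate to pain.

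**6. The inference.** The implied chain runs from microbiota to metabolite to pain. Only the last two links are observed.

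- *Correlation found:* it would look the same whether the metabolite differences arose from microbiota or from something else.
- *No correlation found:* microbiota could still act through products not assayed. Section 1 itself names tryptophan, AhR ligands and tryptamine as microbial products. Tryptophan and tryptamine are not among the seven analytes, and the documents do not identify any of the seven as an AhR ligand or as specifically microbial.

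Either way, the data do not bear on the first link.

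**The case against.** The best defence is that the indirect approach is open. The second aim sentence says how microbiota was to be evaluated, the introduction gives a rationale with references, and the operational target in follow-up item 6 and the SAP is already the narrower correlation. No planned test or sample size depends on the microbiota wording. All of this stands, and it limits the point to the claim attached to the results. It does not remove the point, because disclosing a proxy does not show that it tracks the thing it stands for, and no step in these documents examines that.

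Some stronger readings are tempting but unsupported:

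- *The seven metabolites are an invalid marker of microbiota.* The documents show no validation, but they cite sources that cannot be consulted here. The proxy is undemonstrated, not disproved.
- *No microbiota information was collected at all.* Section 2.2 refers to laboratory results and a data collection form that is not reproduced. What can be said is that none is listed.
- *All four statements claim that gut microbiota affects pain.* Only the second aim sentence says gut, and the methods sentence concerns the cause of metabolite variation.
- *The metabolite–VAS analysis is undermined.* Nothing here affects it.

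The general limits of observational data for causal claims are a separate question. This point rests on the unmeasured exposure alone.

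**Conclusion.** The point holds as a mismatch between claim and measurement, and it should be fixed. Three statements in the title and aim assert an impact or effect of microbiota on pain, and one methods statement assigns metabolite variation to it. Against these stand no listed microbiota data item and no SAP analysis with a microbiota variable. No number in the plan changes.

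The conclusion assumes that the listed data items are complete with respect to microbiota. If the data collection form does hold such a variable, the gap is that neither the Protocol nor the SAP names it or plans an analysis of it.

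**What to change.** 1. Restate the title and both aim sentences as the association between blood kynurenine-pathway metabolites and VAS pain in patients having surgery for lumbar disc herniation. This matches follow-up item 6 and the SAP's sample-size section.
2. In section 2, delete the words that attribute metabolite variation to microbiota, so that the sentence relates the metabolites directly to VAS.
3. Keep microbiota in the introduction as background or as a hypothesised mechanism.
4. Add one limitation sentence, for example: *Microbiota was not measured, and no conclusion about its effect on pain will be drawn from these data.*

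The cost is rewording the title and three sentences and adding one. No sample, procedure or analysis changes. The price is a narrower claim.

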2.1. Data Collection

Blood samples were planned and collected from patients during the preoperative evaluation, at the 8th postoperative hour, and at the 24th postoperative hour, adhering to clinical routines for these procedures. Concurrently with each blood draw, the patient's VAS score, the nature of the pain, and vital signs were recorded. At the end of the surgery, procedures were performed in the recovery unit according to the protocols, and the same data along with vital signs were recorded. Blood samples collected from the patients were centrifuged at 4000 rpm for 10 minutes, after which the serum and plasma portions were transferred to Eppendorf tubes. The blood samples were stored at -80°C for preservation. For the same patients, 24-hour postoperative blood collection was performed, and similar data, including VAS scores, were recorded.

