## Statistical Analysis Plan (SAP)

The Shapiro-Wilk goodness-of-fit test was used to determine whether the distributions of numerical variables conformed to a normal distribution. For numerical variables that followed a normal distribution, descriptive statistics such as mean and standard deviation were provided. For numerical variables that did not follow a normal distribution, descriptive statistics such as median and interquartile range were given. Percentages and frequency tables were provided for categorical variables. To compare the patient and control groups, variables that met the normality assumption were analyzed using the parametric test for the significance of the difference between two means, while those that did not meet the normality assumption were analyzed using the non-parametric Mann-Whitney U test. The assumption of homogeneity of variances was examined with the Levene test statistic. Kruskal-Wallis analysis of variance was used to examine whether there were differences between diagnosis groups in terms of age. The relationship between age and numerical parameters was examined with the Spearman rank correlation coefficient since the age variable did not meet the normality assumption. Whether there were differences in numerical measurements between diagnostic groups was examined with one-way analysis of variance, and when the parametric assumptions of one-way analysis of variance were not met, it was examined with the Kruskal Wallis test. The differences between the groups were examined using the Bonferroni test approach, one of the Post-Hoc tests.

The area under the ROC curve was used to evaluate the performance of the diagnostic test. The Youden index (J), which assumes sensitivity and selectivity, or false positive and false negative rates, as equally important, was used to determine the best cutoff point.

Statistical significance level was accepted as  $p < 0.05$ . Categorical variables are presented as percentages and numbers, and continuous variables are presented as mean (mean), standard deviation (SD) or median, 25th Quarter (Q1) and 75th Quarter (Q3). The suitability of the variables to normal distribution was examined using visual (histogram and probability graphs) and analytical methods (Kolmogorov Smirnov Test). In comparing two independent groups, Mann Whitney U Test was used for those that did not show normal distribution. Spearman correlation analysis was performed to

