evaluate the relationships of continuous variables. In comparing three or more measurements of dependent groups, ANOVA test was used for repeated measurements for data that conformed to normal distribution, and the Friedman test was used for data that did not comply with normal distribution. Wilcoxon test was used for pairwise group comparisons in repeated measurements that were statistically significant. The results were evaluated at a 95% confidence interval, with alpha error set at 0.05. Statistical evaluation was made using the Statistical Package for Social Sciences (SPSS) for Windows 26.0 (IBM SPSS Inc., Chicago, IL) program.

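### The aim is worded as an effect of metabolites on pain, but the planned same-time postoperative correlation with VAS supports only a statement of association

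*Protocol*

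**What the plan says.** **Aim.** The last paragraph of the protocol's Introduction says "we aimed to examine the effect of microbiota and tryptophan metabolites on pain perception in patients undergoing lumbar disc herniation surgery". It continues in the same causal terms: "We evaluated how the gut microbiota affects pain mechanisms by measuring levels of tryptophan metabolites and assessing pain severity".

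**Timing.** Section 2.1 gives the sampling times: "Blood samples were planned and collected from patients during the preoperative evaluation, at the 8th postoperative hour, and at the 24th postoperative hour". It then says "Concurrently with each blood draw, the patient's VAS score, the nature of the pain, and vital signs were recorded". Section 2 also describes pain and vital signs as recorded at the same time as the samples. Section 2 lists an extra sample ("Preoperative, postoperative, 8th-hour, and 24th-hour blood samples were routinely collected from patients"). The two lists should be reconciled, but the difference does not affect this point.

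**Planned evaluation.** Item 6 of the Study Follow-Up Table evaluates the correlation of seven named metabolites "routinely collected in blood samples after lumbar disc herniation surgeries and Visual Analog Scale (VAS) scores".

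**Method.** The SAP sentence that covers metabolite against VAS runs across a page break: "Spearman correlation analysis was performed to", then "evaluate the relationships of continuous variables". It names no time points, lag, change score, baseline adjustment or covariate. The SAP's sample size section also speaks of a correlation between VAS and metabolite measurements.

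**The concern.** The aim has a direction, from metabolite to pain, and the planned coefficient has none. Three mechanisms can produce the same postoperative correlation:

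- the metabolite affects pain;
- pain, or the stress that comes with it, alters the metabolite;
- patients differ in tissue injury or stress response after an operation of more than 2 hours, and that difference shifts both measures.

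If the plan is followed as written, a significant correlation would be reported under an aim that calls it an effect, although the second and third mechanisms can yield the same number. The design does hold one sample taken before the operation and before any postoperative pain, the preoperative draw. The plan does not say that it will be related to later pain.

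**Working it through.** **1. The plan's own figure.** The SAP gives a minimum of 26 patients for effect size r = 0.50, alpha 5%, power 80%, point biserial model. Take the noncentral t with N − 2 degrees of freedom and noncentrality √N · r / √(1 − r²). For N = 26 this is √26 × 0.5 / √0.75 = 2.944, against a two-sided critical value of 2.064, and power is 0.806. N = 25 gives 0.789. So 26 reproduces as a two-sided calculation and is not in dispute. At the 37 surgeries stated in section 2, power for r = 0.50 is 0.927, and the smallest r detectable with 80% power is about 0.43.

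**2. Does any planned method use the order of metabolite before pain?**

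| SAP method | Relates an earlier metabolite value to a later VAS? |
|---|---|
| Spearman, continuous variables | Not stated; no pairing named |
| Spearman, age with numerical parameters | No |
| Repeated-measures ANOVA, Friedman, Wilcoxon | No; they compare repeated measurements with each other |
| Patient-control and diagnosis-group comparisons | No |
| ROC curve and Youden index | No |

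**3. Size of the coefficient with no metabolite effect (illustration).** Let one driver that varies between patients correlate a with both metabolite and VAS, with no other link. The induced same-time correlation is a × a = a². The rejection rate of a two-sided 5% Spearman test at n = 37 was simulated with 4,000 runs per setting. The Pearson check uses Fisher's z, with mean atanh(a²) × √34 compared with ±1.96.

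| a (assumed) | a² | atanh(a²) × √34 | Fisher-z check | Spearman, simulated |
|---|---|---|---|---|
| 0.3 | 0.09 | 0.526 | 8.2% | 7.6% |
| 0.5 | 0.25 | 1.489 | 31.9% | 29.0% |
| 0.7 | 0.49 | 3.126 | 87.8% | 84.3% |

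A second simulation gave 8.3%, 30.0% and 83.8%. A third, with VAS rounded to whole numbers from 0 to 10 (6,000 runs), gave 7.7%, 28.8% and 83.4%.

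**4. The lagged alternative under the same mechanism.** In the third simulation, preoperative metabolite against postoperative VAS, as a partial rank correlation given preoperative VAS, rejected in 5.5%, 4.8% and 5.3% of runs. This is close to the nominal 5% because the preoperative value was taken as independent of the surgical driver.

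**5. What the lagged analysis may cost in power.** Assume a true same-time correlation of 0.50, and a correlation of 0.5 between a patient's preoperative and postoperative metabolite levels. If the preoperative level bears on later pain only through the postoperative level, the lagged correlation is 0.50 × 0.5 = 0.25. From the table in step 3, power at n = 37 is then about 29% to 32%, against 0.927 for r = 0.50. Seven metabolites at two times make 7 × 2 = 14 tests. With Bonferroni, alpha is 0.05 / 14 = 0.0036, z is 2.914, and power is about Φ(1.489 − 2.914) = Φ(−1.425) ≈ 8%.

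**The case against.** Much of this is wording, and that part stands. The study declares itself observational under STROBE, section 2 also speaks of a relationship, and item 6 and the sample size section both say correlation. Recording VAS at the draw is sound measurement for a correlation. The fault lies in attaching causal language to the result.

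Four stronger readings are tempting, and the documents do not support them:

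- *The operation itself creates the correlation.* Every patient has surgery of more than 2 hours. At a fixed time point a shift common to all patients produces no between-patient correlation; only variation in surgical response does.
- *The plan rules out relating preoperative levels to later pain.* The SAP names no pairings, so it is silent on lagged pairs. Item 6 points to post-surgery blood, but section 2 also uses preoperative blood, and the Introduction refers to pain before and after surgery.
- *The false-positive rate is 84%.* That needs one driver to explain 49% of the variance (0.7²) of both measures. Its closeness to the SAP's 0.50 comes only from choosing a = 0.7. At a = 0.3 the rate is about 8%, little above 5%.
- *The preoperative analysis should become the main analysis and carry the effect aim.* Time order leaves stable differences between patients in place. Patients may also already be in pain before surgery, and that pain, or its cause, could influence both the preoperative level and later VAS. Adjusting for a single 0–10 score removes this only in part.

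**Conclusion.** The point holds as a mismatch between a causal aim and an analysis that can show only association. That conclusion rests on the text alone: the wording of the aim, concurrent measurement, and a Spearman correlation with no pairing or adjustment. It needs no assumed value.

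The size is not known from the documents. With no metabolite effect and assumed equal correlations of 0.3, 0.5 and 0.7 with a driver that varies between patients, about 8%, 29% and 84% of studies of 37 patients would show a significant same-time correlation. The data stay usable; what changes is the conclusion they can carry. This is a cheap improvement.

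**What to change.** 1. In the protocol's Introduction and section 2, and in the SAP, state the aim and the conclusion as an association between metabolite levels and VAS. Name the time points paired in each correlation.
2. Add a secondary analysis to the SAP: preoperative level of each metabolite against VAS at the 8th and at the 24th hour, as a partial rank correlation given preoperative VAS, with a stated allowance for 14 tests.
3. The documents are written largely in the past tense. If this analysis is chosen after the data were seen, label it post hoc.
4. Do not report it as proof of an effect, since stable differences between patients and preoperative pain remain.

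**Cost.** Text changes and a little more analysis; the preoperative samples and VAS scores are already in the design. The stated aim becomes less ambitious. The lagged correlation may be weaker than the same-time one and so less well powered, possibly by a large margin under the assumptions shown above. A null lagged result should therefore not be read as evidence of no association.
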